## 1. Introduction

The purpose of this statistical analysis plan (SAP) is to describe the planned analyses and reporting for protocol GBV-102-003, version 2.0 dated 13 November 2019.

This SAP is being written with due consideration of the recommendations outlined in the most recent International Conference on Harmonization (ICH) E9 Guideline entitled Guidance for Industry: Statistical Principles for Clinical Trials and the most recent ICH E3 Guideline, entitled Guidance for Industry: Structure and Content of Clinical Study Reports.

This SAP describes the data that will be analyzed and the subject characteristics, pharmacodynamics, and safety assessments that will be evaluated. This SAP provides details of the specific statistical methods that will be used. The statistical analysis methods presented in this document will supersede the statistical analysis methods described in the clinical protocol. If additional analyses are required to supplement the planned analyses described in this SAP they may be completed and identified in the clinical study report.

## 2. Study Objectives

### Primary Objective:

To evaluate the safety and tolerability of a single intravitreal (IVT) injection of two different dose strengths of GB-102 (1 mg, 2 mg) in subjects with macular edema secondary to diabetic retinopathy (DR) or retinal vein occlusion (RVO) who have received prior induction with anti-vascular endothelial growth factor (VEGF).

### Secondary Objective:

To evaluate the pharmacodynamic response as measured by best corrected visual acuity (BCVA) and central subfield thickness (CST) and time to first rescue injection.

## 3. Study Variables

### Primary Endpoint

#### *Safety*

- Occurrence of ocular and non-ocular adverse events (AE) and serious adverse events (SAE) at all study visits

### Secondary Endpoints

#### *Pharmacodynamic Activity –*

- BCVA (Early Treatment Diabetic Retinopathy Study [ETDRS] protocol) at all study visits
- CST (spectral-domain optical coherence tomography [SD-OCT]) at all study visits
- Observed subjects rescue-free at each study visit
- Time to first rescue injection
- Response to rescue treatment

### Other Variables

- Slit-lamp biomicroscopy

- Dilated ophthalmoscopy
- Intraocular pressure (IOP)
- Physical examination
- Vital signs
- Color fundus photography (CFP)

#### 4. Study Design and Procedures

##### 4.1 General Study Design

This is a Phase 2a, multicenter, open-label, single injection, parallel arm, non-controlled safety, tolerability, and pharmacodynamics study. Eligible subjects will be enrolled to 1 of 2 concurrently initiated open-label GB-102 treatment arms: Group 1: 1 mg (50 µL) and Group 2: 2 mg (50 µL). Subjects will receive the IVT injection of the study drug in the study eye on Day 1.

The planned study assessments (AEs including SAEs, physical examinations, vital signs, BCVA using the ETDRS protocol, slit-lamp biomicroscopy findings, IOP measurements, dilated ophthalmoscopy results, and date of administration of rescue treatment) are conventional parameters used to evaluate the safety of pharmacologic agents in retinal disease. Approximately 20 subjects are planned: 10 subjects treated with 1 mg GB-102 and 10 subjects treated with 2 mg GB-102. There is no pre-set limitation on the proportion of diabetic macular edema (DME) or RVO subjects per dose group. Rescue treatment allowed is any anti-VEGF (aflibercept, bevacizumab, or ranibizumab) and should be used in accordance with the sites standard practice in administering these agents for the treatment of DME or RVO.

Pharmacodynamic activity will be assessed by means of BCVA (using the ETDRS Protocol), retinal CST using SD-OCT, and CFP (including wide field fundus photography, if available).

The null and alternative hypotheses, based on the primary variables, are as follows:

##### 4.2 Schedule of Visits and Assessments

GB-102 will be administered on Day 1 in both Cohorts. Subjects will return to the study center on Days 14, 30, 60, 90, 120, 150, and 180 for safety and clinical assessments. Subjects will exit the study following all study assessments on Day 180.

The schedule of visits and assessments is provided in Table 1 below.

Table 1. Study Plan and Schedule of Assessments

| Activity/Assessment                         | S a | B              | W 2  | M 1  | M 2  | M 3  | M 4   | M 5   | M 6 (ET) |
|---|----------------|----------------|------|------|------|------|-------|-------|----------|
| Visit Day ± Window b             | -30 to -3      | 1              | 14±2 | 30±4 | 60±7 | 90±7 | 120±7 | 150±7 | 180±7    |
| Informed Consent/HIPAA                      | X              |                |      |      |      |      |       |       |          |
| Inclusion/Exclusion Criteria                | X              |                |      |      |      |      |       |       |          |
| Demographics Data                           | X              |                |      |      |      |      |       |       |          |
| Medical/Medication History                  | X              |                |      |      |      |      |       |       |          |
| Physical Examination                        | X              |                |      |      |      |      |       |       | X        |
| Pregnancy Testing c              | X              | X              |      |      |      | X    |       |       | X        |
| Clinical Laboratory Tests d      | X              |                |      |      |      |      |       |       |          |
| Adverse Events                              | X              | X e | X    | X    | X    | X    | X     | X     | X        |
| Concomitant Medications                     | X              | X              | X    | X    | X    | X    | X     | X     | X        |
| Vital Signs f                    | X              | X              |      |      |      |      |       |       | X        |
| BCVA (ETDRS) g                   | OU             | OU             | OU   | OU   | OU   | OU   | OU    | OU    | OU       |
| Slit-lamp Biomicroscopy                     | OU             | OU             | OU   | OU   | OU   | OU   | OU    | OU    | OU       |
| IOP h                            | OU             | OU             | OU   | OU   | OU   | OU   | OU    | OU    | OU       |
| Dilated Ophthalmoscopy                      | OU             | OU             | OU   | OU   | OU   | OU   | OU    | OU    | OU       |
| SD-OCT i                         | OU             | OU             | OU   | OU   | OU   | OU   | OU    | OU    | OU       |
| Intravitreal Depot Photography j |                | SE             | SE   | SE   | SE   | SE   | SE    | SE    | SE       |
| GB-102 Injection k               |                | SE             |      |      |      |      |       |       |          |
| Post-injection Assessment l      |                | SE             |      |      |      |      |       |       |          |
| Follow-Up Call e                 |                | +1 day         |      |      |      |      |       |       |          |

B = Baseline Visit; BCVA = Best Corrected Visual Acuity; ET = Early Termination; ETDRS = Early Treatment Diabetic Retinopathy Study; HIPAA = Health Insurance Portability and Accountability Act; IOP = Intraocular Pressure; M = Month; OU = Both Eyes; S = Screening Visit; SD-OCT = Spectral Domain-Optical Coherence Tomography; SE = Study Eye; V = Visit; W = Week

- a Screening Visit to occur 3 to 30 days before study baseline (Day 1) to ensure that laboratory results are obtained. Imaging eligibility based on SD-OCT will be Investigator determined; there is no reading center confirmation.
- b The protocol-specified procedures for a given study visit may be split across 2 days within the visit-specific window (if applicable); however, for each visit, all BCVA, ophthalmic examinations, and ophthalmic imaging must be performed on the same day and cannot be split across 2 or more days. Evaluations should be performed by the same evaluator for the same subject throughout the study whenever possible. If it is not possible to use the same evaluator to follow the subject, then evaluations should overlap (examine the subjects together and discuss findings) for at least 1 visit.
- c Urine pregnancy test in women of childbearing potential only; additional pregnancy tests may be performed at any time/day during the study.
- d Chemistry (non-fasting blood): hemoglobin A1c.
- e All subjects will receive a telephone call for the day after the intravitreal injection to assess for any significant complaints or adverse events.

- f Heart rate, blood pressure; additional collection of height (without shoes) will be measured at Screening and body weight will be measured at Screening and Month 6/exit.
- g Visual acuity assessment using ETDRS protocol at 4 m with manifest refraction will be performed at all visits; 1 m may be performed if needed.
- h Goldmann applanation tonometry or Tono-Pen acceptable; however, technique used at baseline must be used at all subsequent visits. Intraocular pressure will be checked before dilation and the IVT injection of study drug at dosing visits.
- i Measurements for CST determined by the Investigator (no central reading center confirmation).
- j Wide field color fundus photography (eg, Optos Ultra-widefield or Zeiss Clarius 500 or other ultra-widefield equipment) of the intravitreal GB-102 depot will be obtained following the dilated ophthalmic examination at all visits – if available at the study site. The initial images of the depot should be obtained at baseline (Day 1) **after** the IVT injection of GB-102 and conducted through (and include) the final study visit and any unscheduled visits. The photographs may be used to document the general appearance and rate of bioabsorbability of the depot. If no wide-FOV camera available, standard 30-degree field of view (FOV) imaging documenting the visual axis will be sufficient. For detailed instructions regarding collection of the intravitreal depot CFP imaging, refer to the separately provided guideline.
- k Following intravitreal injection of GB-102, the subject should remain seated for approximately 15 minutes post-injection with minimal to no movement of the head (e.g., bending over, shaking head, laying down) and avoid significant eye movement.
- l Postinjection assessment to consist of checking for count fingers or hand motion vision within 15 minutes after injection; if needed, subject can be examined (eg, additional IOP or ophthalmoscopy, per discretion of the Investigator) prior to going home.

#### 4.3 Masking

This is an open-label study and the injecting investigator/physician may be the assessing investigator. The SD-OCT and CFP technicians and other site personnel, the Sponsor, and CRO are unmasked to treatment assignment.

#### 5. Sample Size

The sample size is within clinical standards for the establishment of preliminary safety of GB-102. The sample size of this study was not selected to support specific statistical hypothesis testing. A sample size of approximately 20 evaluable subjects in the FAS analysis set allows for detection of adverse events with rates that exceed 15% overall and exceed 30% for each dose with approximately 95% confidence.

#### 6. Data Preparation

All reported study data will be recorded on the electronic case report forms (eCRF) supplied by Statistics & Data Corporation (SDC) using iMedNet™. Only the Principal Investigator and authorized study staff according to the Delegation of Responsibilities log are entitled to make entries in the eCRF. After data is entered into the clinical study database, electronic edit checks, and data review will be performed. All data validation specifications and procedures are detailed in the Data Validation Manual as a separate document. When the database has been declared to be complete and accurate, the database will be locked. Any changes to the database after data have been locked can only be made with the approval of the Sponsor and Ora in consultation with SDC.

All analyses outlined in this document will be carried out after the following have occurred:

- All data management requirements are met according to SDC standard operating procedures, including data entry, performance of edit and validation checks, documentation, and resolution of

data queries and database lock with written authorization provided by appropriate SDC and Sponsor personnel.

- Protocol deviations have been identified and status defined (major/minor deviations).
- Analysis sets have been determined.

## 7. Analysis Sets

### 7.1 Safety Analysis Set

The safety analysis set (SS) includes all subjects who received a dose of study treatment. Subjects who receive rescue treatment during the study will be included in the SS. Subjects will be analyzed according to actual treatment received.

### 7.2 Full Analysis Set

The full analysis set (FAS) includes all subjects who received a dose of study treatment and complete a baseline and a post-baseline visit. Subjects will be analyzed according to the actual treatment they received.

### 7.3 Per Protocol

The per protocol (PP) analysis set consists of a subset of the FAS and includes subjects with no major protocol violations that would affect the assessment of the pharmacodynamics, and rescue data.

## 8. General Statistical Considerations

### 8.1 Unit of Analysis

The unit of analysis in this study will be the study eye for all safety and pharmacodynamic summaries. The study eye was selected as the eye that meets all the inclusion criteria and none of the exclusion criteria. If both eyes meet the inclusion and none of the exclusion criteria, the eye with the worst visual acuity at baseline will be selected. If both eyes have the same baseline visual acuity, the right eye will be selected as the study eye. Additionally, non-ocular AEs and medical history will be presented at the subject level. Non-study eye safety summaries will also be presented as appropriate.

### 8.2 Missing or Inconclusive Data Handling

In general, there will be no imputation of missing data other than for partial or missing dates where complete dates are required to flag data as treatment-emergent or concomitant with treatment. Partial/missing start and end dates for AEs and concomitant medications will be imputed as follows:

Partial/missing start date:

- Dates with missing day only will be imputed as the 1st of the month unless the month and year are same as the month and year of first dose of study medication, in which case missing day will be imputed as the first dose day of study medication.

- Dates with both day and month missing will be imputed as 1 Jan unless the year is same as the year of first dose of study medication, in which case missing day and month will be imputed as the first dose day and month of study medication.
- Completely missing dates will not be imputed.

Partial/missing end date:

- Dates with missing day only will be imputed as the last day of the month unless the month and year are the same as the month and year of the last dose of study medication, in which case missing day will be imputed as the last dose day of study medication.
- Dates with both day and month missing will be imputed as 31 Dec unless the year is same as the year of the last dose of study medication, in which case missing day and month will be imputed as the last dose day and month of study medication.
- If the ongoing flag is missing or “Yes” then the date will not be imputed unless death date is available, in which case the missing date will be imputed as the death date. If ongoing is “No” then the missing end date will be imputed as the last dose date.

The original dates will be displayed in data listings and the imputed dates will be used in derivations only (study day, treatment-emergence status, etc).

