A treatment emergent adverse event (TEAE) is an AE with an onset anytime from when the subject has received study drug through 30 days after the study ends whether or not it is considered causally related to the study drug.

Note: AEs must be collected once informed consent has been obtained, regardless of whether or not the subject has been administered study drug.

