#### 13.1 Adverse Events

An adverse event (AE) is defined as any untoward medical occurrence associated with the use of a drug in humans, whether it is considered drug related. An AE can therefore be any unfavorable and unintended medical diagnosis, sign, or symptom; any new undesirable medical occurrence or unfavorable or unintended change in a pre-existing condition that occurs during or after study treatment; or laboratory abnormality, vital sign, or ophthalmic assessment that is assessed as clinically significant and different from baseline (e.g., requiring discontinuation of study treatment, specific treatment, or a change in subject management). If possible, changes in laboratory results or changes in vital signs that meet the definition of an AE should be reported as a medical diagnosis rather than as the abnormal value. All AEs will be coded using MedDRA Version 22.0.

A treatment-emergent adverse event (TEAE) is an AE with an onset anytime from when the subject has received study drug through 30 days after the study ends whether it is considered causally related to the study drug. Adverse events recorded in the eCRF which began prior to treatment will not be included in the summary tables but will be included in the AE data listings. An SAE is any event that involves or results in any of the following outcomes:

- Death
- Life-threatening occurrence (i.e., if in the view of the investigator or Sponsor, the event's occurrence placed the subject at risk of death at the time of the event; it does not refer to an event which hypothetically might have caused death if it were more severe)
- Requires in-patient hospitalization or prolongation of existing hospitalization (hospitalization for elective surgery for a pre-existing condition or for surgery planned before study entry is not considered an SAE)
- A persistent or significant disability/incapacity (permanent or substantial disruption of the subject's ability to perform normal life functions); this definition is not intended to include experiences of relatively minor or temporary medical significance
- Congenital anomaly/birth defect (an AE that occurs in the child or fetus of a subject exposed to study drug prior to conception or during pregnancy)

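### SAP 8.2 sets a partial start date to the dose date without looking at the recorded end date, so an adverse event that ended before dosing can be flagged as treatment-emergent

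*SAP*

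**What the plan says.** SAP 8.2 introduces its date rules with "Partial/missing start and end dates for AEs and concomitant medications will be imputed as follows". Two start-date rules concern dosing:

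- Day missing, month and year equal to those of the first dose: "in which case missing day will be imputed as the first dose day of study medication".
- Day and month missing, year equal to that of the first dose: "in which case missing day and month will be imputed as the first dose day and month of study medication".

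Neither rule has an exception for a recorded end date, and nothing requires the start to be on or before the end. The section closes by saying that "the imputed dates will be used in derivations only (study day, treatment-emergence status, etc"; listings show the dates as recorded.

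SAP 13.1 supplies the definition that uses those dates: "A treatment-emergent adverse event (TEAE) is an AE with an onset anytime from when the subject has received study drug through 30 days" (counted from the end of the study). The end date plays no part in it. The same section also says "Adverse events recorded in the eCRF which began prior to treatment will not be included in the summary tables".

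Pre-dose events are within the collected data. Protocol 8.1 notes that "AEs must be collected once informed consent has been obtained, regardless of whether or not the subject has been administered study drug", and screening takes place 3 to 30 days before Day 1 (Protocol Table 3-1; SAP 4.2).

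**The concern.** Assigning the dose date to a partial onset is a sensible cautious default when the order of onset and dosing is unknown. Here the default also applies when the order is known. If the recorded end date precedes dosing, the onset must precede it too, yet the rule moves the onset to the dose date. The derived record then contradicts the recorded one, and because the definition in SAP 13.1 looks only at onset, nothing later in the derivation corrects it.

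At stake are the tables for the primary endpoint, the occurrence of adverse events. The treatment-emergent flag decides which events appear in them. Safety data are also analysed at the interim once all subjects have completed the 3-month visit (SAP 14). The arms are small, so a single wrongly flagged subject can show in a percentage.

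**Working it through.** The documents state no figure on this point, so there is none to reproduce. The check applies the rules to test dates and then looks at size.

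**1. The rules applied literally.** Assumed dose date: 20 March 2020 (illustrative). The start is imputed by the SAP 8.2 rules, and the event is treatment-emergent if the imputed start is on or after the dose date. The last column adds one condition: an event whose recorded end is before the dose date is not treatment-emergent.

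| Recorded start | Recorded end | Imputed start | Start after end? | Treatment-emergent as written | With end-date condition |
|---|---|---|---|---|---|
| March 2020, day missing | 10 Mar 2020 | 20 Mar 2020 | yes | yes | no |
| 2020 only | 10 Mar 2020 | 20 Mar 2020 | yes | yes | no |
| February 2020, day missing | 10 Mar 2020 | 1 Feb 2020 | no | no | no |
| 2019 only | 10 Mar 2020 | 1 Jan 2019 | no | no | no |
| March 2020, day missing | 25 Mar 2020 | 20 Mar 2020 | no | yes | yes |

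In the first two rows the imputed start is 20 − 10 = 10 days after the recorded end. The last row shows that the condition leaves the cautious default intact where the order is unknown.

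**2. Medications.** SAP 11.2 gives two definitions of a prior medication. One depends on the drug having stopped before study drug, the other on its having been started before study drug. Take a drug with a partial start in March and a stop on 10 March. It is prior by the first definition. By the second it is not, because its imputed start is the dose date. By its recorded stop it was not taken after dosing, so it meets neither limb of the concomitant definition. The result is a start after the stop and conflicting answers on whether the drug is prior.

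**3. Exposure to the day-missing rule.** Let L be the number of pre-dose days over which events are collected. Spread dose dates evenly over a 366-day year and onsets evenly over the L days (both assumptions). In each month, the onsets that fall back into the preceding month number L + (L − 1) + … + 1 = L(L + 1)/2. The share of onsets in the dosing month is therefore about

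1 − 12 × [L(L + 1)/2] / (366 × L) = 1 − 6(L + 1)/366.

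- L = 3: 1 − 24/366 = 93%
- L = 15: 1 − 96/366 = 74%
- L = 30: 1 − 186/366 = 49%

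A full enumeration of dates gives the same rounded values. These are shares of all pre-dose onsets. They are not conditioned on a partial start or on an end before dosing.

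**4. Effect of one record.** With 10 subjects per dose and 20 in total (SAP 4.1), one subject newly counted in a row adds 1/10 = 10 percentage points to the arm and 1/20 = 5 points overall. If the subject already has another event in that row, the subject percentage does not change and only the event count rises.

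**The case against.** The strongest reply is that the SAP already shows the right intent. The opening sentence of SAP 8.2 confines date imputation to cases where a full date is needed to decide the flag, and an end date before dosing decides it without one. SAP 13.1 separately keeps events that began before treatment out of the summary tables. This is fair evidence of intent, but it is not an operating rule. The bullets that follow are unconditional, and the imputed onset is what a program would use to decide whether an event began before treatment.

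It can also be said that the practical effect is slight. Adverse events are queried at screening and again on Day 1, date problems are queried in the database, recorded dates appear in listings, the analysis is descriptive, and the error overcounts events and does not hide them. All of this stands and limits the importance of the point. Queries are not a full safeguard, however: a start in March with an end on 10 March is consistent as recorded, and the contradiction appears only once the start has been imputed.

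Two stronger readings are tempting. A reader might infer that a medication stopped before dosing becomes concomitant. SAP 11.2 does not support this, since such a drug still meets the stop-based definition of prior. A reader might also take the 49% to 93% range as the share of records that would be wrongly flagged. It is not: it ignores whether the start is partial and whether the end precedes dosing, and it varies with the screening lead.

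**Conclusion.** The gap is real and minor. As written, SAP 8.2 combined with SAP 13.1 flags as treatment-emergent an adverse event that meets both of these conditions: its start date is partial and its known parts match the dosing month and year, or the dosing year where only the year is recorded; and its recorded end date precedes dosing. This contradicts SAP 13.1's own exclusion of events that began before treatment. For medications the defect is limited to starts later than stops and unclear classification.

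Few records are likely to meet both conditions, and the documents give no rate from which to estimate the number. The most that one subject can add to a row is 10 percentage points in an arm of 10, and 5 points overall, provided that the subject has no other event in that row. The documents do not support a claim that the primary safety results would be materially inflated. The conclusion assumes that the bullets are programmed as written; a programmer who read the opening sentence of SAP 8.2 as a limit would avoid the error.

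**What to change.** Add this condition to both partial start-date rules in SAP 8.2:

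*Impute the dose date only if the recorded end date (complete, or its recorded parts before any imputation) does not show that the event or medication ended before first dose; otherwise impute the earliest date consistent with the recorded start-date parts, and not later than the recorded end date, and do not flag the event as treatment-emergent.*

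Keep the dose-date rule in all other cases. The test must use the recorded end-date parts, because the end-date rules in the same section can themselves default to the dose date.

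The cost is one sentence in the SAP and one programming condition. No new data are needed and no study procedure changes.
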